If the patient is discharged, follow-up consults will be provided by a palliative care nurse via telephone contact with the patient and/or surrogate, caregiver, or other individuals involved in the patient's care as appropriate. The nurse will assess the patient's physical and mental functioning, review medications and discharge instructions, review the patient's advance care plan and goals of care, respond to patient questions, and identify needs for additional care (procedures outlined in Table 1). The nurse will be provided a semi-structured telephone guide, informed in part by the Re-Engineered Discharge (RED) toolkit supported by Agency for Healthcare Research and Quality²⁸ (**Appendix I**). The initial telephone contact attempt will occur within 96 hours post-discharge. If initial call attempts are unsuccessful, the nurse will continue to contact the patient or other appropriate individuals up to 7 days post-discharge. If the patient and/or surrogate, caregiver, or other individual involved in the patient's care provides verbal permission for the team to send reminder texts or emails regarding the phone consults, and the nurse is unable to reach the individual by phone, the nurse may send text messages or emails. The text or email sent by the nurse will only serve to set up a time to complete the phone call. The nurse will not send sensitive health information via text or email. If unsuccessful after 7 days, the nurse will attempt contact again in 3 weeks (1 month after the scheduled contact). After the initial successful contact, telephone consultations will occur on a flexible schedule (e.g., weekly, bi-weekly, monthly) based on the needs and wishes of the patient, at a minimum frequency of once a month. Both the in-person inpatient consultations and the follow-up telephone contacts will be recorded using standard template forms via Starform in the patient's EMR (**Appendices J, K**).

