During the telephone contact, if a palliative care nurse identifies a need for further care (e.g., referral to hospice, appointment with the outpatient palliative care office, appointment for symptom management, etc.), the nurse will engage the palliative care team and/or the Hepatology team as indicated. Nurses will relay all relevant information from the telephone contacts to the palliative care team and the treating hepatologists via StarPanel and other clinically appropriate communication channels. If the patient is readmitted to the hospital, the inpatient in-person follow-up and outpatient telephone follow-up schedule will restart. Patients will receive inpatient consultations and follow-up outpatient telephone consultations for one year after randomization to the intervention arm or until death.

After completion of the one-year intervention phase, patient participation will be complete. With the exception of the follow-up telephone contacts and patient-friendly materials, similar services are available to all patients per routine practices. There are no other investigational agents or processes being used for the intervention group of patients/providers. See **Figure 4** below for trial design.

[figure not shown]

Figure 4. RCT Study Schema

The palliative care intervention is expected to include:

- Informational, patient friendly Palliative Care Binder, magnet, handout, wallet card
- Establishment of a palliative care plan
- Care coordination by palliative care team
- Early and regular ongoing engagement of palliative care physicians and nurse practitioners for inpatient consultations
- Telephone contacts conducted by trained palliative care nurses to review palliative care plan, assess changes in symptoms, identify patient needs and re-engage the palliative care team or Hepatology team as appropriate for referrals or appointments
- Communication by palliative care team to all providers and teams involved in patient's care
- Systematic collection of information, including identification of surrogate or health care proxy and advance care planning

Inpatient and telephone palliative care consults will consist of a systematic process utilizing standardized template forms and will include all of the components outlined in **Table 1**.

Table 1

Palliative Care Intervention Procedures	Inpatient In-Person Consults	Outpatient Telephone Consults
Introduction to PC	X	
Introduction to concepts of Advance Directive, living will, healthcare agent	X	

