Assess physical and mental functioning	X	X
Review and complete Advance Directives including: review of previously completed advance care directives, discussion/ completion of POST form, code status, and advance care directives (power of attorney, living will, or advance care plan)	X	X
Name surrogate	X	
Review medical history	X	
Review family history	X	
Review social history (marital status, tobacco use, smoking, alcohol use, drug use, occupation, children) and identify patient's barriers to healthcare access	X	
Dignity and Spirituality assessment (referral to chaplain where applicable)	X	X
Review medications and allergies	X	X
Review symptoms*	X	X
Explain medical condition/diagnosis in lay terms and discuss patient's understanding of prognosis	X	
Discuss questions to ask hepatologist	X	X
Discuss social/family support system	X	X
Develop Care Plan and Goals of Care in the context of the patients current medical condition	X	
Review Care Plan and Goals of Care in the context of the patients current medical condition	X	X
Direct/refer patient towards appropriate resources (e.g. hospice where applicable)	X	X
Record time spent with patient	X	X
Ensure family awareness as applicable	X	X
Communication of Care Plan and pertinent information back to Hepatology MD	X	X

*Symptoms include: lack of energy, lack of appetite, pain, dry mouth, weight loss, drowsiness, shortness of breath, constipation, diarrhea, difficulty sleeping, nausea, vomiting, fever, chills, sweats, sore throat, headaches, change in vision, polyuria, polydipsia, cold/heat intolerance, cough, hemoptysis, chest pain, palpitations, orthopnea, hematuria, renal stones, melena, anorexia, enlarged lymph nodes, bleeding, easy bruising, rhinitis, skin reactions, joint pain/swelling, weakness, myoclonus, sadness, agitation, anxiety, confusion, rash

Outcomes

Primary clinical endpoint:

- Time to first hospital readmission within 1-year post randomization

Secondary outcomes are expected to include:

- Days alive out of hospital within 6-months post randomization
- Total days in hospital within 1-year post randomization
- Total days in ICU within 1-year post randomization
- Number of hospital admissions within 1-year post randomization
- Cost of hospital admissions within 1-year post randomization
- Median length of stay per admission
- Number of transfers to hospice within 1-year post randomization
- Time to hospice
- Liver disease-specific health-related quality of life
- Generic measures of quality of life

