7.2 Secondary Outcome Data

Other patient level data will be obtained for this study through retrospective chart review utilizing StarPanel and the RD. Data to be collected include:

- Demographics (e.g., age, sex, race)
- Hospitalizations (date of admission, date of discharge, hospital unit), hospice referrals, and time to hospice placement
- Days alive outside of hospital
- Discharges to hospice
- Date of death (where applicable)
- Clinical interventions, procedures, and events (e.g., surgeries, resuscitation, intubation, ventilator use) extracted from the charts will inform our analyses as to whether initially established palliative care goals of care were met. Examples of met goals could include DNR and advanced care directives being met and whether aggressive treatment has been pursued at the end of life, against the documented wishes of the patient.
- Physical symptoms (e.g., ascites, variceal bleeding, encephalopathy, delirium)
- Liver transplant status (deferred, listed, decline), MELD score, and number of completed liver transplants

Additional secondary outcome data include change of health-related quality of life, as measured by the Chronic Liver Disease Questionnaire (CLDQ),²⁹ change in general quality of life, patient mood, and patient and caregiver satisfaction with care across the study period. Demographic information will also be collected at baseline for all participants and caregivers. Participating hepatology staff will complete a brief survey to provide feedback and gauge satisfaction with intervention procedures.

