We will use PROMIS adult short forms to assess mood in study participants, specifically depression (**Appendix N**) and anxiety (**Appendix O**). Patient Reported Outcomes Measurement Information System (PROMIS) is a system of highly reliable, validated, precise measures of patient-reported health status for physical, mental, and social well-being.³⁴ PROMIS' measures can be used as primary or secondary endpoints in clinical studies of the effectiveness of treatment. The domains of depression and anxiety are measured through four targeted questions each on a 5-point Likert scale. The four items are selected from a full item bank to yield an accurate estimate at a targeted range of the measured domain. Evaluation of construct validity has been accomplished through the specification and testing of hypotheses about the relationship between the PROMIS domain scores, actual clinical status, and other relevant variables. A variety of statistical techniques have been employed to evaluate these hypotheses including mixed-effects models, regression analysis, and structural equation models. Evaluation of construct validity is based on the relationship between the PROMIS scores and other health and clinical measures, and by evaluating known groups' validity.

Hospital Utilization

Days admitted as an inpatient will be compared between the usual care and intervention arm. Admission date, discharge date, and length of stay for inpatient hospitalizations and ICU admissions will be obtained from the Research Derivative. Associated costs and days alive outside of hospital will also be compared between arms.

Survival

Survival rates will be compared between the control and intervention arm one year after study enrollment.

Physical Symptoms

Disease trajectory including diagnoses and physical symptoms (e.g., ascites, variceal bleeding, encephalopathy) will be compared across arms.

Liver Transplant Status

Listing of liver transplant status (deferred, listed, declined), change in MELD score, and the number of completed liver transplants will be compared across arms.

Satisfaction Instruments

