Aim 1: Time to first hospital readmission within 1-year post randomization will be compared across treatment assignment using Cox proportional hazards model, accounting for the competing risk of death and adjusting for relevant demographic and clinical characteristics. A less than 1 hazard ratio for the treatment group status implies reduced readmission rates in the intervention arm given equal mortality rates.

Aim 2: Days alive out of hospital within 6-months post randomization, total days in hospital and ICU within 1-year post randomization, number and cost of hospital admissions within 1-year post randomization, median length of stay per admission, number of transfers to hospice within 1-year post randomization, time to hospice placement after referral, survival, presence of advance directives within 1-year post randomization, presence of physical symptoms, transplant status listing (deferred, listed, declined), and number of completed liver transplants will be obtained via chart review and compared across treatment assignment using proportional odds model for ordinal outcomes, Cox proportional hazards model for time-to-event outcome and logistic regression for binary outcomes, adjusting for relevant demographic and clinical characteristics.

Aims 3 and 4: Both cross-sectional and longitudinal analysis will be conducted to compare between group differences in CLDQ. For the cross-sectional study, for each time point of data collection, linear regression with ordinary least square will be used with CLDQ as the dependent variable (DV) and treatment assignment (0 for control arm and 1 for the intervention arm) as the independent variable (IV) of interest adjusting for baseline CLDQ and potential confounding factors based on clinical and statistical considerations. A positive value of the regression parameter for treatment status indicates higher CLDQ in the intervention arm. For longitudinal analysis, linear mixed model will be adopted including follow-up time and the interaction between follow-up time and treatment group on top of the cross-sectional model. The interaction term is included to compare decreasing rate of CLDQ between groups with a positive value of the corresponding regression parameter indicating slower decline rate of CLDQ in the intervention arm.

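### Physical symptoms are compared between arms from a chart to which the intervention, by schedule, adds symptom reviews, so ascertainment depends on arm

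*Combined protocol and SAP*

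**What the plan says.** **The outcome.** Section 7.2 commits to a between-arm comparison: "Disease trajectory including diagnoses and physical symptoms (e.g., ascites, variceal bleeding, encephalopathy) will be compared across arms". Its data list defines the item by example only: "Physical symptoms (e.g., ascites, variceal bleeding, encephalopathy, delirium". Aim 2 in section 8.0 (Statistical Analyses) repeats it in its list of chart-review outcomes: "presence of advance directives within 1-year post randomization, presence of physical symptoms, transplant status listing (deferred, listed, declined". No closed list of symptoms is given, and Aim 2 attaches no time window to this item, although it does for several of its neighbours.

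**The source.** Section 7.2 states: "Other patient level data will be obtained for this study through retrospective chart review utilizing StarPanel and the RD". Section 7.1 describes the Research Derivative (RD) as holding clinical notes and nursing records as well as codes, laboratory data and encounter data.

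**What the intervention adds to that source.** Of Table 1, section 6.0 says: "Inpatient and telephone palliative care consults will consist of a systematic process utilizing standardized template forms and will include all of the components outlined in" that table. It marks symptom review for both inpatient and telephone contacts, and its footnote begins: "Symptoms include: lack of energy, lack of appetite, pain, dry mouth, weight loss, drowsiness, shortness of breath". Calls take place at least monthly after the first successful contact, until death or one year after randomization. Consults and calls "will be recorded using standard template forms via Starform in the" patient's medical record. Section 7.3 adds that the palliative care provider enters data in structured Starform fields.

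**What usual care gets.** Section 6.0 schedules no palliative care meeting for controls, but allows one if the patient, family or treating physician asks. It also says that services similar to the intervention, other than the calls and printed materials, are routinely available to everyone.

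**The concern.** A chart-review outcome is comparable between randomized arms only if a symptom that is present has about the same chance of being written down in each. Here one arm's treatment consists partly of asking about symptoms on a schedule and filing the answers in the record that will later be abstracted. The outcome is open-ended, and no text tells the abstractor to leave the palliative care notes out.

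A difference in recorded symptoms could then reflect how often patients were asked rather than how their disease progressed. A spurious excess could be reported against the intervention, or a real improvement could be hidden. This concerns one secondary outcome; the primary endpoint, time to first readmission, does not use these data.

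**Working it through.** The documents give no prevalence, effect size or power for this outcome, so there is no stated figure to reproduce. The check has two parts.

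**1. Does the review cover the outcome?** The Table 1 footnote lists 43 items. Set against the four named outcome examples:

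| Outcome example | On the list verbatim? | Overlapping items on the list |
|---|---|---|
| Ascites | No | none obvious |
| Variceal bleeding | No | bleeding, melena |
| Encephalopathy | No | confusion, drowsiness, agitation |
| Delirium | No | confusion, agitation, drowsiness |

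The overlap is partial. It matters because the four are examples only, and an outcome called physical symptoms lets an abstractor count other entries.

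**2. What could unequal capture do?**

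Inputs: n = 200 per arm (section 5.0). Type I error is 0.05 (section 8.0, Power Calculations, stated for the primary endpoint; two-sided is assumed here). True presence and capture rates are assumptions, and true presence is taken as equal in both arms.

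- Recorded presence = true presence × share captured in the chart (a for intervention, b for usual care).
- Odds ratio = [a/(1−a)] / [b/(1−b)].
- Chance of a significant worse result = Φ[(d − 1.96·SE0)/SE1], with d = a − b, p = (a+b)/2, SE0 = √[2p(1−p)/200] and SE1 = √{[a(1−a)+b(1−b)]/200}. This is an unadjusted comparison of two proportions.

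At 50% true presence and 90% capture under intervention, a = 0.45:

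- 90% capture under usual care: b = 0.45, d = 0, odds ratio 1.00, chance Φ(−1.96) = 2.5%.
- 80%: b = 0.40, odds ratio (0.45/0.55)/(0.40/0.60) = 1.23. SE0 = 0.0494 and SE1 = 0.0494, so Φ[(0.05 − 0.0969)/0.0494] = 17%.
- 70%: b = 0.35, odds ratio (0.45/0.55)/(0.35/0.65) = 1.52. SE0 = 0.0490 and SE1 = 0.0487, so Φ[(0.10 − 0.0960)/0.0487] = 53%.

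Varying true presence, with 90% capture under intervention:

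| True presence | Usual-care capture 80%: odds ratio, chance | Usual-care capture 70%: odds ratio, chance |
|---|---|---|
| 30% | 1.17, 10% | 1.39, 29% |
| 50% | 1.23, 17% | 1.52, 53% |
| 70% | 1.34, 30% | 1.77, 81% |

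*Masking.* If the intervention truly lowers presence from 50% to 40%, capture of 90% against 72% removes the difference: 0.40 × 0.90 = 0.36 and 0.50 × 0.72 = 0.36.

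*Reversal.* Suppose a complication is charted only at readmission, in 70% of readmitted patients (assumption), and readmission falls from 60% to 47% (the 13-point reduction in the 60% row of Table 3). Recorded presence is 0.70 × 0.47 = 33% against 0.70 × 0.60 = 42%, an odds ratio of 0.68. The intervention looks better with no change in the complication itself.

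**The case against.** A reader might infer that the intervention will look worse through detection alone. The documents do not support that.

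- None of the four named examples is on the review list. Nothing shows that a complaint noted on a call would be abstracted as encephalopathy or variceal bleeding.
- Everyone is enrolled as an inpatient under a study hepatologist, and patients whose hepatology care is elsewhere are excluded (section 5.0). Major complications may be charted about equally in both arms, so an odds ratio of 1.00 belongs in the range.
- Admissions also generate entries. If the trial's hypothesis of fewer readmissions is right, the bias could favour the intervention.
- The plan gives no rule for interpreting this outcome. Its statements on direction cover Aim 1 and the questionnaires, so it cannot be said that the plan would read an excess as a worse course.

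A reader might also infer that only the intervention arm can have such entries. Usual-care patients may have palliative consults on request; what is unique to the intervention is the scheduling and the calls. The form templates (Appendices J and K) are not in the available text, so a separate field for each of the 43 items cannot be confirmed.

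Finally, CLDQ, EQ-5D-5L and PROMIS are collected on one schedule in both arms (section 7.2), and section 7.3 already treats Starform data as process data.

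All of this limits the claim on direction and size. It does not remove the structural point: the intervention writes on a schedule into the outcome source, and nothing keeps those entries out of the comparison. The questionnaires do not repair a separate chart-based comparison, and using Starform data for process outcomes does not exclude them from abstraction here.

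**Conclusion.** The concern holds in a limited form. Followed as written, the plan makes ascertainment of physical symptoms depend on arm. The likely direction is against the intervention for symptoms that overlap the review. For complications charted mainly at admissions, the bias may be near zero or reversed.

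The size cannot be determined from the documents. The calculations show only that a modest gap in capture could matter with 200 per arm: a 10-point gap gives roughly a one-in-six chance of a falsely significant worse result at 50% true presence, and a 20-point gap slightly more than one in two. Both rest on assumed capture rates, and with equal capture there is no bias. The point should be settled before abstraction, because a between-arm difference in this outcome could not otherwise be read as a difference in disease trajectory.

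**What to change.** In section 7.2 and in Aim 2 of section 8.0 (Statistical Analyses):

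1. Limit this outcome to a listed set of liver complications, over 1 year post randomization.
2. Abstract them from sources that exist in both arms: coded diagnoses and procedures as the anchor, plus hepatology and inpatient physician notes.
3. Exclude palliative care Starforms and nurse-call templates from abstraction of this outcome, and keep them as intervention-arm process data.
4. Rely on CLDQ, EQ-5D-5L and PROMIS for subjective symptoms.

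The cost is a short abstraction rule and an agreed list; the primary endpoint and the care given do not change. A few true symptoms recorded only on a Starform will not be counted.

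The change reduces the asymmetry without removing it. Section 6.0 has nurses relay call findings to the treating hepatologists, so those findings can reach hepatology notes, and coded diagnoses depend partly on readmission. Both should be stated as limitations when the result is interpreted.

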2.0 Rationale and Specific Aims

We will conduct a randomized, controlled study to evaluate the effectiveness of a systematic comprehensive palliative care intervention on patient outcomes in hepatology patients with poor prognosis. Our specific aims are to:

- 1) **Assess the impact of systematic, comprehensive palliative care services compared to usual hepatic care on time to first hospital readmission within 1-year post randomization.**
- 2) **Assess the impact of systematic, comprehensive palliative care services compared to usual hepatic care on other hospital utilization variables (including days alive out of hospital within 6-months post randomization, total days in hospital and ICU within 1-year post randomization, number and cost of hospital admissions within 1-year post randomization, median length of stay per admission, number of transfers to hospice within 1-year post randomization, time to hospice placement, and survival).**
- 3) **Assess the impact of systematic, comprehensive palliative care services compared to usual hepatic care on quality of life.**
- 4) **Assess the impact of systematic, comprehensive palliative care services compared to usual hepatic care on patient satisfaction and caregiver stress and satisfaction.**
- 5) **Evaluate the fidelity of the palliative care intervention and assess the generalizability of implementing a large-scale Palliative Care program.**

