8.0 Statistical Analyses

Power Calculations

Power calculation was conducted on the primary outcome (time to first hospital readmission) using Cox proportional hazards model accounting for competing risk of death.³⁹ Assuming 50% 1-year mortality in both arms of the expected study cohort (‘surprise question’ inclusion which is comparable to a 50% 1-year mortality rate), with type I error of 0.05 and power of 80%, the minimum detectable hazard ratio (HR) under sample size N=400 was calculated given varying hospital readmission rate in the usual care arm ranging from 0.5 to 0.9. The corresponding rate reduction in the intervention arm (DR) and the relative rate reduction (RDR) were also provided. See **Table 3**. To assess clinical rationale of the power calculation, 1-year hospital readmission rate was assessed from pilot data obtained from a retrospective data pull via the Research Derivative. Admission to a study hepatologist during a 3-month window was required for cohort inclusion, and subsequent admission data (1-year post ‘qualifying admission’) was analyzed. Of the 151 patients included in the pilot data, 93 patients (62%) were readmitted within 1 year of the qualifying admission with a 1-year mortality rate of 35%. This pilot cohort (35% mortality rate) may be healthier than expected study cohort. However, due to competing risk of death, we are not sure whether the 1-year readmission rate of 62% from the pilot cohort is an overestimate or underestimate of the target population. Nonetheless, the proposed sample size provides sufficient power (80%) to detect rate reduction

of 13% when the hospital readmission rate in the usual care arm is between 50% and 70%, which is comparable with the pilot data.

Table 3

Various risk of readmission in the usual care arm (R), and the corresponding minimum detectable hazard ratio (HR) and the corresponding inverse HR (1/HR), difference of risk of readmission (DR) and relative difference of the first readmission (RDR) under sample sizes N = 400 with power 80% and type I error 0.05.

N = 400				
R	HR	1/HR	DR	RDR
50%	0.67	1.5	13%	0.26
60%	0.69	1.4	13%	0.22
70%	0.71	1.4	13%	0.18
80%	0.73	1.4	11%	0.14
90%	0.74	1.4	8.3%	0.092

Analyses Plan

Demographic and clinical characteristics of the participants such as age, gender, etc. will be compared between the control and the intervention arms using Wilcoxon rank-sum test for continuous variables and Pearson's Chi-square for categorical variables.

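### Hospice timing is analysed from referral with a Cox model that does not account for death, so its hazard ratio does not show whether more randomised patients reach hospice, or reach it sooner

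*Combined protocol and SAP*

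**What the plan says.** All the analysis text is in section 8.0 (Analyses Plan) of the combined protocol and SAP.

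- **Aim 1** (time to first readmission) uses a Cox model "accounting for the competing risk of death". It makes its reading of a hazard ratio below 1 conditional on the arms having the same mortality.
- **Aim 2** puts hospice timing in one long list with utilisation, survival, symptom and transplant outcomes, worded as "time to hospice placement after referral, survival". The method for the timed outcomes in that list is "Cox proportional hazards model for time-to-event outcome". The paragraph mentions no competing risk and gives no rule for a patient who dies before placement.
- **The time origin differs between sections.** Section 2.0 has "time to hospice placement, and survival" and the Outcomes list in section 6.0 has "Time to hospice". Neither states an origin. Only Aim 2 of section 8.0 starts at referral.
- **Mortality.** The power section works from "Assuming 50% 1-year mortality in both arms of the expected study cohort" and reports 35% in the pilot cohort. Survival is a listed outcome.
- **A related outcome.** Aim 2 also compares the number of transfers to hospice within 1 year of randomisation.

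**The concern.** Death before hospice removes a patient from the possibility of placement. In this population it will probably be common. The intervention could act on both events: Table 1 in section 6.0 includes directing or referring patients to hospice where applicable, and section 1.0 cites evidence that palliative care can lengthen survival.

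When both hazards can move, a hazard ratio for placement with deaths censored answers a narrower question than the one a reader will bring to it. It compares how fast patients still alive and unplaced enter hospice. It does not compare what proportion of each randomised arm gets there.

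The referral origin adds a second restriction. Patients who die, or finish follow-up, without a referral never enter the analysis. Because the intervention can change who is referred and when, the referred patients in the two arms need not be comparable, and randomisation no longer protects the comparison. Adding a competing-risk method without changing the origin would leave that problem in place.

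**Working it through.** **Figures in the plan.** The documents give no hospice rate, referral rate, referral-to-placement interval or target effect for this outcome. Table 3 concerns the primary endpoint only. There is therefore no planned figure to reproduce, and the numbers below are illustrations on assumed rates, with time measured from randomisation. They do not describe the referral-to-placement interval, for which the documents supply no inputs.

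**Model.** Constant hazards over 1 year: h for hospice entry and m for death before hospice.

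Share reaching hospice by 1 year = h/(h+m) × [1 − exp(−(h+m))].

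**Control arm (assumed).** 30% reach hospice and 30% die first. This fits the planned 50% mortality if 20 of every 30 patients who enter hospice also die within the year.

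- h + m = −ln(1 − 0.30 − 0.30) = 0.9163, so h = m = 0.4581.
- Check: 0.5 × (1 − 0.40) = 0.300.

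**Hospice hazard ratio 1.00, m cut by 40%.**

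- m = 0.6 × 0.4581 = 0.2749 and h + m = 0.7330.
- Share = 0.625 × (1 − 0.4804) = 0.325.
- The Cox model shows no effect, while 32.5% versus 30.0% reach hospice.

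**Hospice hazard ratio 0.90, m halved.**

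- h = 0.4123, m = 0.2291 and h + m = 0.6414.
- Share = 0.6429 × (1 − 0.5266) = 0.304.
- The ratio is below 1 although the share is 30.4% versus 30.0%.

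**Hospice hazard ratio 0.90, m unchanged.**

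- h + m = 0.4123 + 0.4581 = 0.8705.
- Share = 0.4737 × (1 − 0.4187) = 0.275.
- The ratio and the share now agree in direction. For a fixed m, the share always rises with h.

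**Range over other assumed control rates, hospice hazard ratio 1.00.** The last two columns give the intervention-arm share when the ratio of the hazards of death before hospice is 0.7 or 1.3.

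| Control reaching hospice | Control dying first | Ratio 0.7 | Ratio 1.3 |
|---|---|---|---|
| 25% | 50% | 27.9% | 22.5% |
| 25% | 35% | 26.8% | 23.4% |

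With 50% dying first, every death in the planned 50% falls before hospice, so this is an upper bound under that mortality. At the other end, with 30% reaching hospice and 10% dying first, cutting the death hazard by 40% gives 30.7% versus 30.0%.

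Across 15–35% reaching hospice and 35–50% dying first, equal shares in the two arms correspond to a hospice hazard ratio of 0.85–0.93 when the death ratio is 0.7, and 1.07–1.17 when it is 1.3. At a hospice hazard ratio of 1.5, the share stayed above control in every scenario tried. The gap therefore matters for hazard ratios near 1, not for large effects.

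**The case against.** A fair defence has four parts.

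1. **A Cox model with deaths censored is not wrong.** This stands. A reader might infer that the censoring is informative and the ratio therefore biased. Read as a cause-specific hazard ratio, it validly compares placement rates among patients alive and unplaced. The limit is on what it can be taken to show.

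2. **No hospice probability is planned.** This also stands. A reader might infer that the trial will overstate hospice use. Under the 30%/30% assumption, one minus a Kaplan-Meier curve with deaths censored would give 1 − exp(−0.4581) = 36.8% against a true 30.0%. But the plan specifies a Cox comparison for hospice timing and no such curve.

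3. **The number of transfers within 1 year already addresses how many patients reach hospice.** This stands in part, so it would be wrong to say that the plan has no view of the question. That outcome carries no timing, has no stated handling of early death, and is not said to be the same event as placement.

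4. **The effects are small and the outcome is secondary.** The 2.5-point difference compares with a standard error of √(0.30×0.70/200 + 0.325×0.675/200) = 4.6 points at 200 per arm. The reversed sign is worth 0.4 points, under one patient per 200, and needs the death hazard halved. If the hazard of death before hospice is equal in the two arms, direction agrees. Equal mortality is the planning assumption, but survival is under test, so the analysis should not depend on it. The planned 50% also includes deaths after hospice entry, so it is a ceiling on the competing-event rate, not an estimate of it.

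**Conclusion.** The point holds in a limited form. The hospice-timing analysis omits the competing risk that Aim 1 takes into account, and it starts from referral, an event after randomisation that sections 2.0 and 6.0 do not mention. As written, its hazard ratio cannot by itself show whether more randomised patients reach hospice, or reach it sooner, when death before hospice differs by arm.

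Under the assumed rates the discrepancy is modest: 32.5% versus 30.0% at a hazard ratio of 1.00 in the main illustration, and 0.7 points when only 10% of controls die first. These sizes rest on constant hazards and on hospice rates that the documents do not supply. Reading the point as a biased hazard ratio, as overstated hospice probabilities, or as a threat to the primary analysis would go beyond the text.

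**What to change.** In section 8.0, Aim 2:

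- Define time to hospice from randomisation, in all randomised patients, and align sections 2.0 and 6.0 with that definition.
- Treat death without hospice as a competing event. Name the method explicitly, because Aim 1 does not say whether its ratio is cause-specific or subdistribution.
- Report cumulative incidence of hospice by arm and the 1-year difference with a 95% interval, with the cumulative incidence of death without hospice beside it.
- The Cox hazard ratio may stay alongside if it is labelled cause-specific. Any referral-to-placement interval should be descriptive only.

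Section 7.2 already collects hospice referrals, time to hospice placement, discharges to hospice and date of death. The cost is a few sentences, a check that placement can be dated from randomisation, and a small amount of extra analysis. Sample size and the primary analysis are unaffected.
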